### Introduction

Internet usage has increased greatly. It is expected to be more than 4 billion by the end of this year(1). About 80% of them spend most of their internet time on social media, and are expected by 2026 to be about 50% of the total population to use social media at least once a month(1). The internet is mainly used to connect with friends, relatives, learn new skills, or for entertainment, such as video gaming (2). However, with this increasing usage, internet addiction can easily increase.

Internet addiction or pathological internet use is defined as uncontrolled, excessive use of it, with uncontrolled time consuming that can cause distress, and impairment (3,4). The prevalence of internet addiction varied between regions. A study in the seven countries in Europe reported a prevalence of addiction among adolescents to be 1%, and an additional 12.7% at risk of having addiction(5). In Turkey, a recent cross-sectional study conducted by Sayili et al found a prevalence of 18.3% (6). In the Middle East, the prevalence varied greatly from 0.9% to 33% among adolescents (7–9). For Egypt, Ibrahim et al, 2020 assess the prevalence of internet addiction among undergraduate medical students in Assiut University. They collected data from 321 students, revealing a prevalence being 9%. They also found a statistical association between internet addiction and increasing depression among these students(10). Sayed et al, 2022 was another cross-sectional study that was conducted among pharmacy students in Egypt. They also found a prevalence being 38.5%. They also found a statistically significant association between internet addiction and stress, depression and anxiety.(11)

Additionally, internet video gaming is another addictive problem that can affect adolescents. A previous meta-analysis showed that gaming addiction prevalence ranged from 0.9% to 19.9%, with males being higher than females(12). Also, Pitanupong et al 2025 showed a prevalence of about 8.4% among Thailand medical students. (13). Shouman et al 2023 was a cross-sectional study conducted among university students in Egypt at Mansoura university. They found a 6% prevalence among these students. Again,

they found a statistically significant association between gaming addiction and psychological factors. (14)

On the other hand, overuse of the internet can lead to an increase in problematic pornography use. Karim et al. 2025(15) found a significant association between increased usage of the internet and pornography addiction (P value: <0.001). Additionally, previous studies showed a prevalence of porn addiction ranging from 3.2% to 16.6%(16). Also, a negative correlation between education level and porn addiction was observed.(17).

All these behavioral addictions increase depression, anxiety, and stress for addicts. Several cross-sectional studies have assessed the positive correlation between either internet, gaming, or porn addiction, and an increase in anxiety and depression. (6,10,13,15,18) However, to our knowledge, no single study has assessed these three addictive behaviors together with depression, anxiety, and stress in Arab countries.

#### Rational

Medical students, in particular, use the internet frequently. They use it in training, faculty assignments, research projects, and so on, which can make them depend greatly on the internet. This potentially can increase their addiction to the internet, subsequently increasing their addiction to video gaming and porn addiction. (19). In the Middle East, few studies have tried to assess the prevalence of internet addiction and its association with increased depression, anxiety, and stress(7,9,18) among medical students. Despite that, there is a lack of studies on gaming addiction and porn addiction.

We aim to assess the prevalence of internet addiction alongside video gaming and porn addiction among medical students and interns in the Middle East (MENA region). We also aim to assess the relationship of these three addictive behaviors with each other and their relationship with increased stress, anxiety, and depression among this population.

### **Research Questions**

- 1. What is the prevalence of internet, gaming, and porn addiction among medical students in the MENA region?
- 2. What is the prevalence of stress, anxiety, and depression among this population?
- 3. What is the relation between these types of addictions and the level of stress, anxiety, and depression among this population?

### Aim

To assess the prevalence of internet, gaming, and porn addiction among medical students in the Middle East region to help improve their quality of life.

## **Objective**

- 1. To assess the prevalence of internet, gaming, and porn addiction among Medical students and interns in the MENA region
- 2. To assess the prevalence of anxiety, depression, and stress among this population.
- 3. To assess the relation between these addictions and depression, anxiety, and stress.

# Methodology

# **Technical Design**

- 1. Study design: Cross-sectional study
- 2. **Setting**: Medical students in some Middle East countries (Egypt, Sudan, Somalia, Libya, Morocco, United Arab Emirates, Jordan, Syria, Yemen, Iraq, and Palestine)
- 3. **Time**: From July 2025 to December 2025
- 4. **Population**: Arabic Medical students in the MEAN region

### 5. Inclusion Criteria

- Arabic Medical students and interns
- Studying medicine in the Middle East countries
- Have access to online platforms
- Agree to participate in the study

### 6. Exclusion Criteria

• Students or interns who refused to participate

### 7. Sampling

We calculated the total sample size using Epi Info version 7.2.60(*Epi InfoTM* | *CDC*, n.d.) Assuming a 50% prevalence rate and a 5% error margin with a 95% confidence interval, the sample size required for each country is 383. After adding a 10% nonresponse rate, the final sample size is about 422 for each country, so the total sample size will be 4642

8. Sampling Technique: Convenience Sampling

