### **Operational design**

- 1. **Pilot**: We will perform a pilot study in each country before starting the study to assess the readiness of the questions and the reliability of the questions via the Cronbach's alpha test.
- 2. **Study field**: an online questionnaire will be shared via an online platform with the target population.

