#### 3. Data collection method

An online questionnaire will be shared via social media platforms such as Facebook, WhatsApp, and Telegram.

The questionnaire is composed of 8 sections as follows:

- The first section provides a brief introduction to the topic, its importance in the research field, and consent to participate in the study.
- ➤ In the second section, sociodemographic data will be collected, such as age, gender, type of university, smoking level, number of sleeping hours, difficulty in accessing the internet, and reason for using internet platforms
- In the third section, we will ask about internet addiction. We will use the Internet Addiction Scale (IAT) (21,22) This scale is a 20-question Likert scale, and each question has six answer scales from 0 to 5 (Not applicable, rarely, occasionally, frequently, often, and always). This makes a range of scores from 0 to 100.

- The participants can be classified into normal usage, mild, moderate, and severe levels of addiction if they score (0-30), (31-49), (50-79), and (80-100), respectively.
- ➤ In the fourth section, Gaming addiction will be assessed. We will use the Internet Gaming Disorder Scale—Short-Form (IGDS9-SF) (23,24)

  This scale consists of a 9-question Likert Scale. Each question has five answers, scored from 1 to 5. Total score ranges from 9 to 45, with a higher score indicating a higher level of gaming disorder.
- ➤ We used the GAD-7 scale (25,26) in the fifth section to assess the level of anxiety. This scale consists of a 7-question Likert scale, each one has four answers scored from 0-3, making a range of scores from 0-21.

  Students can be classified into minimal, mild, moderate, and severe levels of anxiety if they score (0-4), (5-9), (10-14), and (15-21), respectively.
- ➤ In the sixth section, we used the Patient Health Questionnaire-9 (PHQ-9) (26,27)to assess the level of depression.
   A 9-question Likert scale with four answers for each question. Scores range from 0-3, making the range of scores from 0-27.
   Students can be classified into minimal, mild, moderate, moderately severe,
  - and severe levels of depression if they score (0-4), (5-9), (10-14), (15-19), and (20-27), respectively.
- ➤ In the seventh section, we asked about stress level through the Perceived Stress Scale-10 (PSS-10) (Ali et al., 2021; Cohen et al., 1983). A 10-question Likert Scale, and each question has 5 answers, which score from 0-4. A total score ranges from 0-40.

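### The 5% margin behind 383 per country is nominal under convenience recruitment through social media and does not cover selection, yet Objective 1 is worded for the whole region

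*Protocol*

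**What the plan says.** Protocol, Technical Design, section 7 (Sampling), gives the only statement of precision: "Assuming a 50% prevalence rate and a 5% error margin with a 95% confidence interval, the sample size required for each country is 383". A 10% non-response allowance raises this to about 422 per country and 4642 in total. Item 8 then reads "Sampling Technique: Convenience Sampling".

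The Data collection method section states how respondents are reached: "An online questionnaire will be shared via social media platforms such as Facebook, WhatsApp, and Telegram". Operational design says that "an online questionnaire will be shared via an online platform with the target population". Among the inclusion criteria is "Have access to online platforms".

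The first objective is "To assess the prevalence of internet, gaming, and porn addiction among Medical students and interns in the MENA region". The Statistical analysis section plans frequencies and percentages, group comparisons, correlations and a multiple linear regression. It plans no confidence interval for a prevalence.

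**The concern.** A margin of error at a given confidence level says how far an estimate may stray because of random selection. It has that meaning when selection probabilities are known, as in a simple random sample or another probability sample with a design effect near 1. A convenience sample recruited by a shared link has no known selection probabilities. The target of 422 in each country allocates numbers between countries but leaves selection within a country undefined.

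For one of the three addictions, the recruitment channel also lies close to the outcome. Among eligible students, the chance of meeting and answering a social-media link may depend on time spent online, which is related to internet addiction. If response depends on the outcome in either direction, the resulting error does not shrink as numbers grow, and the 10% allowance for non-response adds respondents without addressing it.

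At stake is how the prevalence is read. Objective 1 claims it for students and interns across the region. The design describes those with online access, in the 11 listed countries, who chose to respond. A reader who takes the 5 points from section 7 as delivered precision would put too much trust in the figure.

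**Working it through.** **1. The plan's own figures.** Inputs from section 7: prevalence 0.50, margin d = 0.05, 95% confidence (z = 1.96), 10% non-response. The Setting lists 11 countries.

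- n = z² p(1−p)/d² = 1.96² × 0.25 / 0.05² = 384.2. The Protocol has 383. A finite-population correction would explain the small difference (382.7 at an assumed population of 100,000; 383.4 at 200,000), but no population size is given.
- 383 × 1.10 = 421.3, about 422.
- 422 × 11 = 4642.

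The arithmetic is sound. The formula contains only random-sampling variance, with no term for a design effect or for selection.

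**2. What selection could do (illustration).** Let p be the true prevalence and k the probability of response among addicted students divided by that among the others. No document bounds k; the values below are assumptions. The prevalence expected among respondents is

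p′ = kp / (kp + 1 − p).

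With n = 383, SE = √(p′(1−p′)/n) and bias b = p′ − p, the coverage of p′ ± 1.96 SE for the true p is, by normal approximation,

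Φ(1.96 − b/SE) − Φ(−1.96 − b/SE).

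Worked case, p = 0.50 and k = 1.1: p′ = 0.55/1.05 = 0.5238; b = 2.38 points; SE = 2.55 points; b/SE = 0.933; coverage 84.6%.

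| True p | k = 0.8 | k = 0.9 | k = 1 | k = 1.1 | k = 1.25 |
|---|---|---|---|---|---|
| 50% (planning value) | 41.0% | 82.2% | 95.0% | 84.6% | 41.0% |
| 20% (assumed) | 58.3% | 86.9% | 95.0% | 88.4% | 58.3% |
| 9% (Introduction, Egyptian medical students) | 76.0% | 90.9% | 95.0% | 91.7% | 76.0% |

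**3. Bias against the fixed 5 points.** The k at which bias alone equals the margin is odds(p ± 0.05)/odds(p).

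| True p | k for +5 points | k for −5 points |
|---|---|---|
| 50% | 1.22 | 0.82 |
| 20% | 1.33 | 0.71 |
| 9% | 1.65 | 0.42 |

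On both yardsticks the effect is weaker at low prevalence.

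**4. Larger n does not help.** At p = 0.50 and k = 1.1 the bias stays at 2.38 points. With n = 4 × 383 = 1532, SE is 1.28 points and coverage falls to about 54%. With 11 × 383 = 4213 pooled without weights, SE is 0.77 points and coverage is about 13%, while the nominal margin shrinks to 1.5 points.

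**The case against.** The best defence is that nothing is hidden. Convenience sampling is declared, and section 7 introduces the 5% as a planning assumption rather than a promised result. Because no interval for prevalence is planned, the coverage figures describe an analysis that the Protocol does not specify. Eligibility already requires online access, so students without it are outside the study population. The Rational section says "Medical students, in particular, use the internet frequently", and the link is meant for the target population; both may weaken selection on time online. Weighting or sensitivity analyses may sit in a statistical analysis plan that is not shown. The largest losses of coverage arise at the planning value of 50%, whereas every prevalence of addiction cited in the Introduction is lower, the highest being 38.5% in pharmacy students.

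Most of this stands, and it limits the point. The coverage figures are conditional illustrations, and the absence of weighting is not counted as a fault. What it does not answer is that section 7 never says the margin loses its meaning under the sampling method named in the next item, and that Objective 1 is not narrowed to match the design.

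A reader might infer that the survey will overestimate internet addiction because heavy users see the link more often. The documents do not support that: overestimation is plausible, but selection the other way is possible. Nor does the argument about time online carry over directly to gaming or pornography; for those outcomes the point is only that the margin is nominal. A reader might also infer that 383 is miscalculated or that only simple random sampling would do. Neither follows: the figure reproduces, and any probability sample with a design effect of about 1 or less would deliver the margin.

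**Conclusion.** The concern holds as a mismatch between the stated precision and the fixed recruitment method. The 5% margin is nominal: it reflects sampling error under random selection, does not cover selection, and cannot be restored by reaching 383 or 422 per country. The practical size cannot be derived from the Protocol. Under assumed response ratios of 1.1 and 1.25, a nominal 95% interval would hold about 85% and 41% of the time at a true 50%, 88% and 58% at 20%, and 92% and 76% at 9%. These figures rest on the assumed k, n = 383, a normal approximation, and an interval that the Protocol does not itself plan. The change is worth making because it costs almost nothing and alters what the study can claim.

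**What to change.** 1. In section 7, state that 383 is a planning figure under a random-sampling assumption, and that under convenience recruitment the 5% margin is nominal and not a delivered precision.
2. Word Objective 1 and the conclusions as prevalence among responding medical students and interns with online access in the participating countries, not among the MENA student population as a whole.

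Both are wording changes; they need no extra participants and no new items. The price is a less favourable precision statement and a narrower claim. The rewording does not remove selection. The items already collected on "difficulty in accessing the internet, and reason for using internet platforms" describe the respondents, but they are known only for those who answer and so cannot show how non-respondents differ.

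### The 10% non-response allowance multiplies 383 by 1.10 instead of dividing by 0.90, so 422 per country yields about 380 responders, 3 fewer than the stated requirement (very small effect)

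*Protocol*

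**What the plan says.** The sample size is set in the protocol under Technical Design, item 7 (Sampling). The per-country requirement comes first: "Assuming a 50% prevalence rate and a 5% error margin with a 95% confidence interval, the sample size required for each country is 383". The next sentence applies the allowance and gives the total: "After adding a 10% nonresponse rate, the final sample size is about 422 for each country, so the total sample size will be 4642".

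The multiplier for the total is the country list in item 2 (Setting), which has 11 entries: "Egypt, Sudan, Somalia, Libya, Morocco, United Arab Emirates, Jordan, Syria, Yemen, Iraq, and Palestine".

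Two other statements bear on what 422 can mean. Item 8 reads "Sampling Technique: Convenience Sampling", and the data collection section of the Operational design says: "An online questionnaire will be shared via social media platforms such as Facebook, WhatsApp, and Telegram". The protocol describes no list or count of people invited, and it does not say whether 422 counts people approached or questionnaires completed.

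**The concern.** A non-response allowance turns the number of responders needed into the number of people to approach. Because the rate applies to those approached, the conversion divides by the expected response proportion. Adding 10% to the responder target instead applies the rate to the wrong base and always gives too small a number.

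Here the two adjacent sentences do not agree with each other. One states a requirement of 383. The other states a size that, at the stated non-response rate, does not deliver it. What is at stake is the correctness of the sample size statement, which anyone reading it can recompute. No test, estimate or decision in the protocol is built on 422 or 4,642.

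**Working it through.** **Inputs, all from the protocol.** Prevalence 50%, margin 5 percentage points, 95% confidence, 383 required per country, 10% non-response, about 422 per country and 4,642 in total (item 7, Sampling); 11 countries (item 2, Setting).

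**1. The base figure.** For a single proportion, n = z² × p(1 − p)/d² = 1.96² × 0.25/0.05² ≈ 384.15 (385 if rounded up). The stated 383 is slightly lower. It is what a finite-population correction gives for a population of roughly 100,000 to 200,000: 382.7 at 100,000, 383.2 at 150,000 and 383.4 at 200,000. The protocol gives no population size, so that range is an assumption. The 383 is accepted here as the stated requirement.

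**2. Reproducing the stated sizes.**
- 383 × 1.10 = 421.3, rounded up to 422. This matches.
- 422 × 11 = 4,642. This matches, so the total is a correct product that carries the per-country figure forward; it is not a second error.

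**3. What 422 delivers if it is the number before non-response.**
- Per country: 422 × 0.90 = 379.8, about 380, against 383.
- All countries: 4,642 × 0.90 = 4,177.8, against 383 × 11 = 4,213. The difference is 35.2, or 0.8%.
- Non-response that 422 can absorb while still leaving 383: 1 − 383/422 = 9.2%, not 10%.

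**4. The size that meets the requirement.**
- 383/0.90 = 425.6, so 426 per country. Check: 426 × 0.90 = 383.4.
- 426 × 11 = 4,686, which is 44 more than 4,642 (0.9%).

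**5. Effect on precision.** The half-width of the 95% interval at p = 0.5, under simple random sampling and without a finite-population correction, is 1.96 × √(0.25/n):

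| Responders per country | Half-width |
|---|---|
| 383 | 5.01% |
| 380 | 5.03% |

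The change is 0.02 percentage points.

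**The case against.** The best counter-argument is that the sentence does what it says: it adds 10% to 383 and reports the result as approximate, so there is no miscalculation, only a simpler way of inflating. The protocol also calls 422 the final size, admits only people who agree to take part, and recruits through an open link with no count of invitees. On that basis 422 could be a target for completed questionnaires, and then nothing falls short. Finally, the deficit of 3 is close to the imprecision already in the base figure (383 against 384 or 385 from the uncorrected formula), and both margins round to the stated 5%.

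Much of this stands. The shortfall depends on reading 422 as the number before non-response, which the wording implies but does not state. With convenience sampling through an open link, non-response could not be observed against any known number approached. The effect on precision is negligible.

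What does not stand is the claim that the method is a matter of taste. An allowance for non-response makes sense only if the inflated number is the one before non-response, and on that footing dividing by 0.90 follows from what the rate means. The word about covers rounding 421.3 to 422; it does not cover the step from 422 to 426. A target for completed questionnaires would need no allowance, so the sentence would still have to be reworded.

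**Conclusion.** The point holds, as a minor correction. The allowance was applied by multiplication where division is needed, and the stated final size misses the protocol's own requirement by about 3 responders per country, or about 35 in total (0.8%). The nominal margin becomes 5.03% instead of 5.01%.

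The shortfall rests on three conditions: 422 is the number before non-response, the 10% rate is met exactly, and 383 is taken as the requirement. If 422 means completed questionnaires, the shortfall disappears and only the wording is at fault. The margins are nominal in either case, because they assume simple random sampling while the plan uses a convenience sample.

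**What to change.** Rewrite the sentence in one of three ways, and say in it what the number counts:

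- **Correct the number:** 383/0.90 = 426 per country, 4,686 in total. This raises the target by 4 per country, 44 overall.
- **Keep the number:** retain 422 and 4,642 as the sizes before non-response, and state that 10% non-response leaves about 380 responders per country, with a nominal margin of 5.03% under simple random sampling. This adds no recruitment but openly accepts a yield 3 below 383.
- **Redefine the number:** if 422 is the target for completed questionnaires, say so and remove the reference to non-response. This also adds no recruitment.

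Each option costs one line of protocol text, and no analysis step has to change.

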### **Operational design**

- 1. **Pilot**: We will perform a pilot study in each country before starting the study to assess the readiness of the questions and the reliability of the questions via the Cronbach's alpha test.
- 2. **Study field**: an online questionnaire will be shared via an online platform with the target population.

#### 3. Data collection method

An online questionnaire will be shared via social media platforms such as Facebook, WhatsApp, and Telegram.

The questionnaire is composed of 8 sections as follows:

- The first section provides a brief introduction to the topic, its importance in the research field, and consent to participate in the study.
- ➤ In the second section, sociodemographic data will be collected, such as age, gender, type of university, smoking level, number of sleeping hours, difficulty in accessing the internet, and reason for using internet platforms
- In the third section, we will ask about internet addiction. We will use the Internet Addiction Scale (IAT) (21,22) This scale is a 20-question Likert scale, and each question has six answer scales from 0 to 5 (Not applicable, rarely, occasionally, frequently, often, and always). This makes a range of scores from 0 to 100.

- The participants can be classified into normal usage, mild, moderate, and severe levels of addiction if they score (0-30), (31-49), (50-79), and (80-100), respectively.
- ➤ In the fourth section, Gaming addiction will be assessed. We will use the Internet Gaming Disorder Scale—Short-Form (IGDS9-SF) (23,24)

  This scale consists of a 9-question Likert Scale. Each question has five answers, scored from 1 to 5. Total score ranges from 9 to 45, with a higher score indicating a higher level of gaming disorder.
- ➤ We used the GAD-7 scale (25,26) in the fifth section to assess the level of anxiety. This scale consists of a 7-question Likert scale, each one has four answers scored from 0-3, making a range of scores from 0-21.

  Students can be classified into minimal, mild, moderate, and severe levels of anxiety if they score (0-4), (5-9), (10-14), and (15-21), respectively.
- ➤ In the sixth section, we used the Patient Health Questionnaire-9 (PHQ-9) (26,27)to assess the level of depression.
   A 9-question Likert scale with four answers for each question. Scores range from 0-3, making the range of scores from 0-27.
   Students can be classified into minimal, mild, moderate, moderately severe,
  - and severe levels of depression if they score (0-4), (5-9), (10-14), (15-19), and (20-27), respectively.
- ➤ In the seventh section, we asked about stress level through the Perceived Stress Scale-10 (PSS-10) (Ali et al., 2021; Cohen et al., 1983). A 10-question Likert Scale, and each question has 5 answers, which score from 0-4. A total score ranges from 0-40.
  - Students can be classified into mild, moderate, and severe levels of stress if they score (0-13), (14-26), and (27-40), respectively.
- Finally, the eighth section will ask about porn addiction. The Problematic Pornography Consumption Scale (PPCS) (29) will be used, which consists of an 18-question Likert Scale. Each question consists of 7 answers, and

their scores range from 1-7. A total score ranges from 18-126, with higher levels indicating a higher level of porn addiction. A 76 score will be used as a cut-off value to indicate a high risk of porn addiction.

We used the Arabic version alongside the English version of the validated questionnaire because some Arabic countries did not teach medicine in English so the English will be a challenge for them.

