## 4. Statistical analysis

First, data will be summarized according to its type. Categorical data will be summarized using frequency and percentage. Continuous data will be tested for normality. if the data is normally distributed, we will summarize it using mean and SD, and if not, median and IQR will be used. We will assess the difference between the population according to their sociodemographic data using a Chi-square and a Mann-Whitney U test. A p-value of <0.05 will be used as a cutoff point for statistically significant results. We will assess the correlation between all continuous data (internet addiction, gaming, porn addiction, stress, depression, and anxiety levels). Finally, a multiple linear regression test will be used to assess the relationship between the assessed variables.

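### Does the missing IGDS9-SF case rule mean the protocol cannot deliver its gaming-addiction prevalence?

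*Protocol*

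**What the plan says.** The protocol promises a gaming prevalence in four places. Objective 1 is "To assess the prevalence of internet, gaming, and porn addiction among Medical students and interns in the MENA region". Research Question 1 asks "What is the prevalence of internet, gaming, and porn addiction among medical students in the MENA region", the Aim repeats it, and the Rational section says "We aim to assess the prevalence of internet addiction alongside video gaming and porn addiction among medical students and interns". The Rational section also gives a reason for the study: "Despite that, there is a lack of studies on gaming addiction and porn addiction".

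Section 3 (Data collection method) describes the IGDS9-SF as nine items scored 1 to 5 and cites two papers for it, one on its development and one on an Arabic validation. Its only scoring statement beyond that is "Total score ranges from 9 to 45, with a higher score indicating a higher level of gaming disorder". The same section gives four bands for the IAT (the lowest being normal usage), four for the GAD-7 and five for the PHQ-9 (the lowest being minimal in both), three for the PSS-10 (mild 0-13, moderate 14-26, severe 27-40), and a cut-off of 76 for the PPCS.

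Section 4 (Statistical analysis) summarises categorical data by frequency and percentage, and continuous data by mean and SD or by median and IQR. It then adds: "We will assess the correlation between all continuous data (internet addiction, gaming, porn addiction, stress, depression, and anxiety levels").

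**The concern.** A prevalence needs a rule that separates cases from non-cases, and for gaming the protocol prints none. Read alone, it lets the gaming score be summarised by a mean or median but not by a percentage of cases. The gaming figures in the Introduction (0.9% to 19.9%, 8.4% and 6%) are all case percentages, so a mean score could not be set beside them in the Discussion. A cut-off chosen after the scores are seen could also largely determine the result. Because section 3 classifies the other five scales, the gap looks like an oversight.

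A second worry concerns stress. The PSS-10 bands start at mild, so even a total of 0 carries a stress label. If every labelled level counted as stress, the prevalence in Objective 2 would be 100% whatever the data.

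**Working it through.** **1. How many totals section 3 classifies.** The inputs are the ranges and bands printed there. For the PPCS, 76 itself is taken to lie on the high-risk side.

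| Scale | Possible totals | Given a class |
|---|---|---|
| IAT, 0-100 | 101 | 31 + 19 + 30 + 21 = 101 |
| IGDS9-SF, 9-45 | 37 | 0 |
| GAD-7, 0-21 | 22 | 5 + 5 + 5 + 7 = 22 |
| PHQ-9, 0-27 | 28 | 5 + 5 + 5 + 5 + 8 = 28 |
| PSS-10, 0-40 | 41 | 14 + 13 + 14 = 41 |
| PPCS, 18-126 | 109 | 58 below 76, 51 from 76 up = 109 |

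The omission for the IGDS9-SF is real.

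**2. A class is not a case.** To report one prevalence per condition, the protocol would have to say which classes count.
- PPCS: one explicit threshold, worded as high risk.
- IAT: normal usage implies a non-case group, but nothing says that mild counts as addiction.
- GAD-7 and PHQ-9: no statement of whether cases start at mild, at moderate or higher.
- PSS-10: no statement of which band or bands count.
- IGDS9-SF: no bands at all.

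By this test only one of the six scales is fully specified. Gaming has least detail, but it is not the only scale lacking a case rule.

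**3. The continuous list.** The correlation sentence in section 4 names all six scores, including the banded IAT and the PPCS with its cut-off. Gaming's place in that list therefore does not show that it will go unclassified.

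**4. The 100% reading of the PSS-10.** The three bands do cover all 41 totals. But the GAD-7 bands are likewise described as levels of anxiety, from minimal to severe, and cover all 22 totals. Read as literally, anxiety prevalence would also be 100%. No section pools the bands on either scale. Section 4 reports categories as frequencies and percentages, and renaming the lowest PSS-10 band would move no participant between bands.

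**5. How much a rule matters.** The documents give no score distributions, so these are assumptions for illustration. With normal IGDS9-SF scores (mean 16 to 20, SD 7 to 8), the share at or above an arbitrary threshold c is 1 - Φ((c - 0.5 - mean)/SD):
- c = 21: 26.0% to 47.5%
- c = 27: 6.7% to 20.8%
- c = 32: 1.3% to 7.5%
- c = 36: 0.3% to 2.6%

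With normal PSS-10 scores (mean 18 to 22, SD 6), moderate or worse is 77% to 92% and severe alone is 8% to 23%. The choice of rule clearly matters, but nothing in the documents selects one.

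**6. Sample size.** Section 7 (Sampling) assumes 50% prevalence, a margin of 5 points and 95% confidence: n = 1.96² × 0.5 × 0.5 / 0.05² = 384.1. The stated 383 matches this with a finite-population correction (382.7 for an assumed population of 100,000; 383.4 for 200,000). Then 383 × 1.10 = 421.3, rounded up to 422, and 422 × 11 countries = 4642. Since p(1 - p) is largest at 50%, any case rule gives a margin no wider than planned. With 383 respondents, 1.96 × √(p(1 - p)/383) is 2.4 points at 6% and 2.8 points at 8.4%, the two Introduction figures for university and medical students.

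**The case for a change.** The strongest case for a change is that the gap is an internal mismatch, visible without any analysis plan. The protocol chose to fix scoring in section 3, did so for five scales, and left out the one scale whose under-studied condition helps justify the study. For the PPCS it cites the source and also prints the cut-off, so a citation alone was evidently not thought enough. A rule fixed in advance would cost a line of text and would remove any suspicion that the cut-off was chosen to suit the data.

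Much of this stands. The IGDS9-SF has no printed rule, and step 5 shows that the result would be sensitive to one. What does not stand is the inference that the plan must change. Whether the two papers cited for the scale carry a case rule cannot be checked here, and neither can an analysis plan that may supply one. That a cut-off might be picked late is a possibility, not something the protocol says. The documents support no particular rule, so the most a revision could require is that some rule be written down, which reporting any gaming percentage requires anyway. The fallback, giving up the prevalence in favour of the score distribution, would remove an objective without improving the study.

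**Conclusion.** The observation is accurate: 0 of 37 IGDS9-SF totals are classified, while Objective 1 asks for a gaming prevalence. It is a missing detail that analysts fill as a matter of course, and not a fault in the design. Nine item responses per participant are collected, so a case rule can be applied to the data in full. The sample size (383, 422 and 4642) and the correlation and regression work under Objective 3 are unaffected.

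Two stronger readings fail. Gaming is not the only scale without a stated case rule, since the IAT, GAD-7, PHQ-9 and PSS-10 also leave open which bands count. The 100% stress prevalence arises only by pooling bands that the protocol does not pool; calling the lowest PSS-10 band low instead of mild would be optional wording that alters no percentage.

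The conclusion rests on two assumptions: that the case definitions will be stated before the data are examined, in the analysis plan or an equivalent record, and that each reported percentage will name the bands or cut-off behind it. No shift in any prevalence can be claimed, because the documents give no score distribution for either scale.
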